5.2 SAFETY PARAMETERS AND DEFINITIONS

Safety assessments will consist of monitoring and recording adverse events, including serious adverse events that are deemed critical to the safety evaluation of the study.

Certain types of events require immediate reporting to the Sponsor, as outlined in Section [5.4](#).

5.2.1 Adverse Events

According to the ICH guideline for Good Clinical Practice, an adverse event is any untoward medical occurrence in a clinical investigation subject administered a

pharmaceutical product, regardless of causal attribution. An adverse event can therefore be any of the following:

- Any unfavorable and unintended sign (including an abnormal laboratory finding), symptom, or disease temporally associated with the use of a medicinal product, whether or not considered related to the medicinal product
- Any new disease or exacerbation of an existing disease (a worsening in the character, frequency, or severity of a known condition) (see Sections [5.3.5.5](#) and [5.3.5.6](#) for more information)
- Recurrence of an intermittent medical condition (e.g., headache) not present at baseline
- Adverse events that are related to a protocol-mandated intervention

5.2.2 Serious Adverse Events (Immediately Reportable to the Sponsor)

A serious adverse event is any adverse event that meets any of the following criteria:

- Is fatal (i.e., the adverse event actually causes or leads to death)
- Is life threatening (i.e., the adverse event, in the view of the investigator, places the patient at immediate risk of death)

This does not include any adverse event that, had it occurred in a more severe form or was allowed to continue, might have caused death.

- Requires or prolongs inpatient hospitalization (see Section [5.3.5.7](#))
- Results in persistent or significant disability/incapacity (i.e., the adverse event results in substantial disruption of the patient's ability to conduct normal life functions)
- Is a congenital anomaly/birth defect in a neonate/infant born to a mother exposed to study drug
- Is a significant medical event in the investigator's judgment (e.g., may jeopardize the patient or may require medical/surgical intervention to prevent one of the outcomes listed above)

The terms "severe" and "serious" are not synonymous. Severity refers to the intensity of an adverse event (e.g., rated as mild, moderate, or severe, or according to NCI CTCAE; see Section [5.3.3](#)); the event itself may be of relatively minor medical significance (such as severe headache without any further findings).

Severity and seriousness need to be independently assessed for each adverse event recorded on the eCRF.

Serious adverse events are required to be reported by the investigator to the Sponsor immediately (i.e., no more than 24 hours after learning of the event; see Section [5.4.2](#) for reporting instructions).

5.3 METHODS AND TIMING FOR CAPTURING AND ASSESSING SAFETY PARAMETERS

The investigator is responsible for ensuring that all adverse events (see Section 5.2.1 for definition) are recorded on the Adverse Event eCRF and reported to the Sponsor in accordance with instructions provided in this section and in Sections 5.4–5.6.

The investigator is also responsible for reporting medical device complaints (see Section 5.4.4).

For each adverse event recorded on the Adverse Event eCRF, the investigator will make an assessment of seriousness (see Section 5.2.2 for seriousness criteria), severity (see Section 5.3.3), and causality (see Section 5.3.4).

5.3.1 Adverse Event Reporting Period

Investigators will seek information on adverse events at each patient contact.

All adverse events, whether reported by the patient or noted by study personnel, will be recorded in the patient's medical record and on the Adverse Event eCRF.

After informed consent has been obtained, all adverse events should be reported from Day 1 visit of this study until the end of the study. For ongoing adverse events which occurred before the Day 1 visit of this study, the adverse event will be reported as outlined in Section 5.1.

Instructions for reporting adverse events that occur after the adverse event reporting period are provided in Section 5.6.

5.3.2 Eliciting Adverse Event Information

A consistent methodology of non-directive questioning should be adopted for eliciting adverse event information at all patient evaluation timepoints. Examples of non-directive questions include the following:

"How have you felt since your last clinic visit?"

"Have you had any new or changed health problems since you were last here?"

5.3.3 Assessment of Severity of Adverse Events

The adverse event severity grading scale for the NCI CTCAE (v5.0) will be used for assessing adverse event severity. [Table 2](#) will be used for assessing severity for adverse events that are not specifically listed in the NCI CTCAE.

Table 2 Adverse Event Severity Grading Scale for Events Not Specifically Listed in NCI CTCAE

Grade	Severity
1	Mild; asymptomatic or mild symptoms; clinical or diagnostic observations only; or intervention not indicated
2	Moderate; minimal, local, or non-invasive intervention indicated; or limiting age-appropriate instrumental activities of daily living ^a
3	Severe or medically significant, but not immediately life-threatening; hospitalization or prolongation of hospitalization indicated; disabling; or limiting self-care activities of daily living ^{b, c}
4	Life-threatening consequences or urgent intervention indicated ^d
5	Death related to adverse event ^d

NCI CTCAE = National Cancer Institute Common Terminology Criteria for Adverse Events.

Note: Based on the most recent version of NCI CTCAE (v5.0), which can be found at:

http://ctep.cancer.gov/protocolDevelopment/electronic_applications/ctc.htm

- ^a Instrumental activities of daily living refer to preparing meals, shopping for groceries or clothes, using the telephone, managing money, etc.
- ^b Examples of self-care activities of daily living include bathing, dressing and undressing, feeding oneself, using the toilet, and taking medications, as performed by patients who are not bedridden.
- ^c If an event is assessed as a "significant medical event," it must be reported as a serious adverse event (see Section 5.4.2 for reporting instructions), per the definition of serious adverse event in Section 5.2.2.
- ^d Grade 4 and 5 events must be reported as serious adverse events (see Section 5.4.2 for reporting instructions), per the definition of serious adverse event in Section 5.2.2.

5.3.4 Assessment of Causality of Adverse Events

Investigators should use their knowledge of the patient, the circumstances surrounding the event, and an evaluation of any potential alternative causes to determine whether an adverse event is considered to be related to the study drug administered in the parent study, indicating "yes" or "no" accordingly. The following guidance should be taken into consideration (Table 3):

Table 3 Causal Attribution Guidance

Is the adverse event suspected to be caused by the study drug administered in the parent study on the basis of facts, evidence, science-based rationales, and clinical judgment?	
YES	There is a plausible temporal relationship between the onset of the adverse event and administration of the study drug, and the adverse event cannot be readily explained by the patient's clinical state, intercurrent illness, or concomitant therapies.
NO	An adverse event will be considered related, unless it fulfills the criteria specified below. Evidence exists that the adverse event has an etiology other than the procedure (e.g., preexisting medical condition, underlying disease, intercurrent illness, or concomitant medication); and/or the adverse event has no plausible temporal relationship to the initiation of a study procedure.

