5. ASSESSMENT OF SAFETY

5.1 SAFETY PLAN

Any adverse events that occur during this study should be reported as outlined below.

For ongoing adverse events starting in the parent study, any follow-up of the adverse event will be reported in this study (Study CV43140). The adverse event severity, according to NCI CTCAE v5.0 ([Table 2](#)), should be evaluated by the investigator at the Day 1 visit of this study and recorded in the "adverse event initial NCI CTCAE grade" field of the Adverse Event eCRF for Study CV43140. The most extreme NCI CTCAE grade for the adverse event should also be recorded, taking into account the severity of the event since it was first reported during the parent study.

Please note that "study drug" refers to the treatment administered in the parent study prior to this follow-up study.

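### Table 3 asks whether the parent-study drug caused the event, but both criteria for answering NO refer to a procedure, so the two rows overlap and leave gaps

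*Combined protocol and SAP*

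**What the plan says.** Section 5.3.4 directs the investigator "to determine whether an adverse event is considered to be related to the study drug administered in the parent study", with a yes or no answer guided by Table 3. The question at the top of the table names the same drug. The YES row requires that "There is a plausible temporal relationship between the onset of the adverse event and administration of the study drug", and that the event is not readily explained by the patient's clinical state, intercurrent illness or concomitant therapies.

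The NO row opens with a default: "An adverse event will be considered related, unless it fulfills the criteria specified below". Two criteria follow, joined by and/or. The first is "Evidence exists that the adverse event has an etiology other than the procedure", with these examples: "preexisting medical condition, underlying disease, intercurrent illness, or concomitant medication". The second is that "the adverse event has no plausible temporal relationship to the initiation of a study procedure".

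Two kinds of event reach this table:

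- **Carried-over events.** Section 5.1 states: "For ongoing adverse events starting in the parent study, any follow-up of the adverse event will be reported in this study". Their grade at Day 1 goes in a "field of the Adverse Event eCRF for Study CV43140". Section 5.3 requires a causality assessment for each event recorded on that form.
- **Procedural events.** Section 5.2.1 counts events related to a protocol-mandated intervention as adverse events.

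**The concern.** The test is stated five times in section 5.3.4. Three statements (section text, table question, YES row) name the drug, and two (both NO criteria) name a procedure. The terms are not interchangeable in this protocol. Section 5.1 defines study drug as the parent-study treatment, section 4.3 says none is given in CV43140, section 1.2 uses procedure for venipuncture and swabs, and section 5.5.1 lists study treatment and trial-related procedures as separate sources of relatedness. No section says that a procedure includes the drug, and none corrects the table.

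At stake is the investigator's yes or no on drug causality. Under section 5.6 that answer is one basis for reporting requirements. Under section 5.5.1 it decides whether a serious event gets the additional effort to follow it to a final outcome. The NO row is the only text that defines when an event is not related, and about 180 sites (section 9.5) could resolve the conflict differently.

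**Working it through.** The plan gives no figure to reproduce, so the check applies the printed rules to test cases.

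**Rules as printed**

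- YES = plausible drug timing AND not readily explained by clinical state, intercurrent illness or concomitant therapies.
- NO = evidence of a cause other than the procedure OR no plausible timing to a study procedure.
- Default = related if NO is not met.

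**Event A: an event ongoing from the parent study, with plausible drug timing and no other ready explanation.** YES is met. For NO, the answer depends on two points that the documents leave open:

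| Meaning of study procedure | Etiology criterion read literally (the drug is a cause other than the procedure) | Etiology criterion read as excluding the drug |
|---|---|---|
| CV43140 procedures only | NO met on both criteria | NO met on timing |
| Parent-study procedures too, with the event plausibly timed to one | NO met on etiology | NO not met |

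The top row follows from dates. A carried-over event began before Day 1 (5.3.1), and consent must precede the first CV43140 assessment, at Day 1 at the latest (3.1), with the first samples scheduled at Day 1 (Appendix 1). Such an event cannot be plausibly timed to a CV43140 procedure. Three of the four readings give both YES and NO. The literal column treats the grounds for suspecting the drug as evidence of etiology.

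**Event B: an injury from the Month 6 blood draw (scheduled in Appendix 1), with no plausible drug timing and no evidence of another cause.** YES fails on timing. NO fails on both criteria, because the cause is the procedure and the timing fits it. The default makes the event related, under a question about the drug.

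**Event C: plausible drug timing, none of the listed explanations, but evidence that a study procedure caused it.** This case tests the correction. As printed, YES is met, because procedures are not in its list of other explanations. NO is not met, so the answer is YES only.

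**Effect of rewording**

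| Event | As printed | NO row changed to the drug | NO row changed, and study procedure added to the YES row's list |
|---|---|---|---|
| A | YES and NO (three of four readings) | YES only | YES only |
| B | Neither; defaults to related | NO only | NO only |
| C | YES only | YES and NO | NO only |

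Changing the NO row alone settles A and B but creates a new overlap at C. The addition to the YES row closes it. The last column takes a ready explanation in the YES row and evidence of another etiology in the NO row to be the same test.

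**The case against.** The strongest reply is that investigators will see what was meant. Table 3 is guidance, its question names the drug, and section 5.3.4 also relies on knowledge of the patient and clinical judgment. The bracketed examples in the NO row are all causes other than the drug, which points to a drafting slip. To miscode event A, an investigator who suspects the drug would have to answer NO because the event did not follow a CV43140 procedure. That is unlikely, and the point stands as a limit on practical risk. It does not remove the conflict in the printed rule.

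A reader might infer that a drug-related serious event coded NO would go unreported or unfollowed. The documents do not support that:

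- Section 5.4 requires serious events to reach the Sponsor within 24 hours whatever their relationship to the drug.
- Section 5.5.1 requires follow-up of each adverse event until it resolves, is stable, or the patient is lost or withdraws consent, regardless of causality.
- Section 5.5.2 lets the Sponsor pursue any serious event and assess it independently.
- Section 5.6 has the Sponsor evaluate all serious events and allows it to upgrade the assessment.

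Only the additional effort for related serious events depends on the answer.

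A reader might also infer that every carried-over event gets a contradictory answer. That goes too far. Under the CV43140 reading all of them meet the NO timing criterion, but for those with a cause other than the drug, NO is the right answer. The double answer concerns only those with plausible drug timing and no other ready explanation.

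**Conclusion.** The inconsistency is real and should be corrected. Table 3 asks about one object and defines NO by another, so its rows can both apply or both fail.

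The timing overlap for carried-over events assumes that a study procedure means a CV43140 procedure, a term the documents do not define. The etiology overlap assumes a literal reading of the first NO criterion. The blood-draw case needs neither assumption about the rows' wording; it needs only that the event has no plausible drug timing and no evidence of another cause.

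The size cannot be expressed as a rate, because the documents give no adverse event counts by cause. The consequence is limited to investigator causality coding and its two uses, in sections 5.6 and 5.5.1. It would be wrong to infer biased study results: the primary endpoint is a descriptive summary of the symptom diary (6.4.1), and the planned adverse event summaries (6.5) do not depend on attribution.

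**What to change.** Make three wording changes in Table 3:

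1. In the first NO criterion, replace the procedure with the parent-study drug.
2. In the second NO criterion, replace the start of a study procedure with administration of that same drug.
3. In the YES row, add study procedure to the list of other explanations.

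The section text, question and both rows then refer to the same object.

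These changes remove the only wording in section 5.3.4 that bears on procedures. Sections 5.2.1 and 5.5.1 both recognise procedure-related events, and section 5.4.4 covers events from the wearable. If relatedness to procedures or the device is wanted, it should be a separate question on the form.

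The cost is a short wording change and a site memo. If events have already been assessed under the present table, sites should recheck those causality entries, starting with events carried over from the parent study. A separate procedure or device question, if adopted, would add a field to the form.

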5.3.5 Procedures for Recording Adverse Events

Investigators should use correct medical terminology/concepts when recording adverse events on the Adverse Event eCRF. Avoid colloquialisms and abbreviations.

Only one adverse event term should be recorded in the event field on the Adverse Event eCRF.

5.3.5.1 Diagnosis versus Signs and Symptoms

A diagnosis (if known) should be recorded on the Adverse Event eCRF rather than individual signs and symptoms (e.g., record only liver failure or hepatitis rather than jaundice, asterixis, and elevated transaminases). However, if a constellation of signs and/or symptoms cannot be medically characterized as a single diagnosis or syndrome at the time of reporting, each individual event should be recorded on the Adverse Event eCRF. If a diagnosis is subsequently established, all previously reported adverse events based on signs and symptoms should be nullified and replaced by one adverse event report based on the single diagnosis, with a starting date that corresponds to the starting date of the first symptom of the eventual diagnosis.

5.3.5.2 Adverse Events That Are Secondary to Other Events

In general, adverse events that are secondary to other events (e.g., cascade events or clinical sequelae) should be identified by their primary cause, with the exception of severe or serious secondary events. A medically significant secondary adverse event that is separated in time from the initiating event should be recorded as an independent event on the Adverse Event eCRF. For example:

- If vomiting results in mild dehydration with no additional treatment in a healthy adult, only vomiting should be reported on the eCRF.
- If vomiting results in severe dehydration, both events should be reported separately on the eCRF.
- If a severe gastrointestinal hemorrhage leads to renal failure, both events should be reported separately on the eCRF.
- If dizziness leads to a fall and consequent fracture, all three events should be reported separately on the eCRF.
- If neutropenia is accompanied by an infection, both events should be reported separately on the eCRF.

All adverse events should be recorded separately on the Adverse Event eCRF if it is unclear as to whether the events are associated.

5.3.5.3 Persistent or Recurrent Adverse Events

A persistent adverse event is one that extends continuously, without resolution, between patient evaluation timepoints. Such events should only be recorded once on the Adverse Event eCRF. The initial severity (intensity or grade) of the event will be recorded at the time the event is first reported. If a persistent adverse event becomes

more severe, the most extreme severity should also be recorded on the Adverse Event eCRF. If the event becomes serious, it should be reported to the Sponsor immediately (i.e., no more than 24 hours after learning that the event became serious; see Section 5.4.2 for reporting instructions). The Adverse Event eCRF should be updated by changing the event from "non-serious" to "serious," providing the date that the event became serious, and completing all data fields related to serious adverse events.

A recurrent adverse event is one that resolves between patient evaluation timepoints and subsequently recurs. Each recurrence of an adverse event should be recorded as a separate event on the Adverse Event eCRF.

5.3.5.4 Deaths

All deaths that occur during the protocol-specified adverse event reporting period (see Section 5.3.1), regardless of relationship to study drug, must be recorded on the Adverse Event eCRF and immediately reported to the Sponsor (see Section 5.4.2). This includes death attributed to progression of COVID-19.

Death should be considered an outcome and not a distinct event. The event or condition that caused or contributed to the fatal outcome should be recorded as the single medical concept on the Adverse Event eCRF. Generally, only one such event should be reported. If the cause of death is unknown and cannot be ascertained at the time of reporting, "**unexplained death**" should be recorded on the Adverse Event eCRF. If the cause of death later becomes available (e.g., after autopsy), "unexplained death" should be replaced by the established cause of death. The term "**sudden death**" should not be used unless combined with the presumed cause of death (e.g., "sudden cardiac death").

If the death is attributed solely to progression of COVID-19, "COVID-19 progression" should be recorded on the Adverse Event eCRF.

Deaths that occur after the adverse event reporting period should be reported as described in Section 5.6.

5.3.5.5 Preexisting Medical Conditions

A preexisting medical condition is one that is present at the screening visit for the parent study. Such conditions should be recorded on the General Medical History and Baseline Conditions eCRF and where possible, will be transferred from the parent study.

A preexisting medical condition should be recorded as an adverse event only if the frequency, severity, or character of the condition worsens during the study. When recording such events on the Adverse Event eCRF, it is important to convey the concept that the preexisting condition has changed by including applicable descriptors (e.g., "more frequent headaches").

5.3.5.6 Lack of Efficacy or Worsening of COVID-19

Medical occurrences or symptoms of deterioration that are anticipated as part of COVID-19, such as fluctuations in symptoms should not be recorded as adverse events. However, deterioration that is judged by the investigator to have unexpectedly worsened in severity or frequency or changed in nature at any time during the study should be recorded as an adverse event. When recording an unanticipated worsening of COVID-19 on the Adverse Event eCRF, it is important to convey the concept that the condition has changed by including applicable descriptors (e.g., "accelerated worsening of COVID-19").

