Only medically-attended visits related to COVID-19, as determined by the investigator, will be recorded in the eCRF. Details will include at minimum:

- Type of visit (hospitalization, ER visit, urgent care visit, physician's office visit, or telemedicine visit)
- Date of visit
- Primary reason for COVID-19–related medically-attended visit

- Treatments given for COVID-19 (including, but not limited to, concomitant medications and supplemental oxygen)
- If hospitalization due to COVID-19 was required, include length of visit, whether intensive care unit care was given, or whether mechanical ventilation was required

Any adverse events or concomitant therapies reported to the investigator should be recorded on the respective Adverse Events eCRF or Concomitant Medications eCRF.

4.5.6 Optional Blood Samples for Whole Genome Sequencing or Whole Exome Sequencing (Patients at Participating Sites)

At participating sites, optional blood samples will be collected from consenting patients for DNA extraction to enable Whole Genome Sequencing (WGS) or whole exome sequencing (WES) to identify variants that are predictive of response to study drug, are associated with progression to a more severe disease state, are associated with susceptibility to developing adverse events, can lead to improved adverse event monitoring or investigation, or can increase the knowledge and understanding of disease biology and drug safety. Of note, at participating sites, blood samples will only be collected from consenting patients who have not previously provided a WGS sample in the parent study. Research will be aimed at exploring inherited characteristics. The samples may be sent to one or more laboratories for analysis.

Collection and submission of blood samples for WGS or WES is contingent upon the review and approval of the exploratory research by each site's IRB/EC and, if applicable, an appropriate regulatory body. If a site has not been granted approval for WGS or WES, this section of the protocol (Section [4.5.6](#)) will not be applicable at that site.

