6.4.2 Secondary Endpoints

The secondary endpoints are as follows:

- Impact of dyspnea symptoms on specific activities, as assessed through use of PROMIS-Dyspnea Questionnaire at Day 1 and Months 1, 2, 3, 4, 5, and 6
- Respiratory-specific health-related quality of life, as assessed through use of SGRQ at Day 1 and Months 1, 2, 3, 4, 5, and 6
- Proportion of patients with COVID-19-related medically-attended visits through to study end (defined as hospitalization, ER visit, urgent care visit, physician's office visit, or telemedicine visit with the primary reason for the visit being COVID-19 or COVID-19-related symptoms)
- Proportion of patients with all-cause mortality

- Proportion of patients with death attributable to progression of COVID-19
- Proportion of patients re-infected with SARS-CoV-2
- Proportion of patients with any post-treatment infection including but not limited to bacterial, viral, or fungal pneumonia or sepsis
- Frequency of COVID-19-related complications (e.g., death, hospitalization, radiologically-confirmed pneumonia, acute respiratory failure, sepsis, coagulopathy, pericarditis, myocarditis, cardiac failure)
- Incidence and severity of adverse events and serious adverse events, with severity determined according to NCI CTCAE v5.0

Observed absolute values will be summarized by means, standard deviations, medians, and ranges for continuous endpoints, as appropriate, while count and percentages will be tabulated for categorical endpoints by study timepoints. Longitudinal modeling of endpoints may also be explored, as appropriate.

All endpoints will be summarized descriptively and no p-values will be presented.

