Appendix 1: Schedule of Activities (cont.)

- ^d The COVID-19 Symptom Diary will be completed by the patient every week, with a 7-day recall of symptoms at worst. This questionnaire should be completed within 48 hours when the window for completion opens every 7 days. The PGIS will be completed every week at the same time as the COVID-19 Symptom Diary for the duration of the study.
- ^e All details to be recorded in the eCRF at all visits. For details of the assessment, see Section [4.5.5.3](#).
- ^f The symptom-guided NP swab for COVID-19 RT-PCR, genetic analysis, and BioFire® assay is to be conducted at any visit or UV, when the investigator determines it is warranted. Symptom-guided defined as patient with any “COVID-19 like” symptom(s) (see [Appendix 2](#) for example symptoms). Patients should immediately contact the site upon onset of any “COVID-19 like” symptom(s) to ensure timely collection of appropriate samples.
- ^g At least two NP swabs, one from each nostril, will be taken and sent to a central laboratory, as clinically indicated. Results from NP swabs will not be available during the study. Therefore, if a COVID-19 re-infection is suspected, it is under investigator’s discretion to perform a local diagnostic test.
- ^h The symptom-guided serum sample for biomarkers and SARS-CoV-2 antibodies is to be conducted at any visit or UV, when the investigator determines it is warranted. Symptom-guided defined as patient with any “COVID-19 like” symptom(s) (see [Appendix 2](#) for example symptoms). Patients should immediately contact the site upon onset of any “COVID-19 like” symptom(s) to ensure timely collection of appropriate samples.
- ⁱ Not applicable for a site that has not been granted approval for WGS or WES. Performed only for patients at participating sites who have provided written informed consent to participate and have not previously provided a blood sample for WGS in the parent study. If the sample is not collected at the Day 1 visit for any reason, it may be collected at any later timepoint.
- ^j Depending on local and country regulations and allowances, patients will be provided with a consumer-grade wearable device (e.g., Apple Watch) where possible at the Day 1 visit to use on a continuous basis. Patients will be provided information regarding the use of the device (e.g., charging, waterproof properties, and support). Data stored in the wearable device will be uploaded through a smart device preferably on a daily basis.

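### Seven of the nine listed COVID-19 complications have no stated data source, and the adverse event rule lets sites leave anticipated ones unrecorded

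*Combined protocol and SAP*

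**What the plan says.** - **Endpoint (Table 1 and Section 6.4.2).** The secondary endpoint is "Frequency of COVID-19-related complications (e.g., death, hospitalization, radiologically-confirmed pneumonia, acute respiratory failure, sepsis, coagulopathy, pericarditis, myocarditis, cardiac failure"). No form, time window or adjudication is given. Section 6 leaves endpoint details to a SAP that is to be finalized before study completion.
- **Exclusion (Section 5.3.5.6).** Medical occurrences and symptoms of "deterioration that are anticipated as part of COVID-19, such as fluctuations in symptoms should not be recorded as adverse events".
- **Exception (same paragraph).** An adverse event is to be recorded for "deterioration that is judged by the investigator to have unexpectedly worsened in severity or frequency or changed in nature".
- **Deaths (Section 5.3.5.4).** All deaths in the reporting period go on the Adverse Event eCRF. "This includes death attributed to progression of COVID-19".
- **Medically-attended visits (Section 4.5.5.3).** "Only medically-attended visits related to COVID-19, as determined by the investigator, will be recorded in the eCRF". The minimum content is visit type, date, primary reason and treatments. For admissions it adds: "If hospitalization due to COVID-19 was required, include length of visit, whether intensive care unit care was given, or whether mechanical ventilation was required". Appendix 1 schedules the assessment at Day 1, at Months 1 to 6 and at early termination or unscheduled visits: "All details to be recorded in the eCRF at all visits".

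**The concern.** An endpoint that counts diagnoses such as myocarditis or coagulopathy needs somewhere for the diagnosis to be written down. The form most likely to hold it carries a rule that turns away COVID-19 occurrences regarded as anticipated. The protocol itself labels these diagnoses as COVID-19-related complications, so a site could reasonably regard one of them as anticipated, follow Section 5.3.5.6 to the letter, and leave an endpoint event off the form.

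Any error goes in one direction, toward too few complications, and its size depends on how each site reads an undefined word. Section 9.5 plans about 180 sites for about 1040 patients, or 1040/180 = 5.8 patients per site, so that judgment is spread thinly over many investigators. Section 6.1 says the study is designed for estimation, so an ascertainment error passes directly into the reported frequency. A later SAP cannot recover events that were never entered.

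**Working it through.** **No plan figure to reproduce.** The 1040 patients come from site feasibility (Section 6.1). The documents state no complication rate, precision target or test. The check is therefore a comparison of the recording rules, followed by an illustration of size.

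**Step 1: where can each component be recorded?**

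| Component | Route that Section 5.3.5.6 does not close | Otherwise |
|---|---|---|
| Death | Section 5.3.5.4: always on the Adverse Event eCRF | not needed |
| COVID-19 hospitalization | Section 4.5.5.3: medically-attended-visit form | not needed |
| Seven diagnoses: pneumonia confirmed by imaging, acute respiratory failure, sepsis, coagulopathy, pericarditis, myocarditis, cardiac failure | Partial: the visit form's primary-reason and treatment fields, if there was a visit and the investigator called it COVID-19-related. No diagnosis field is specified | Adverse Event eCRF, subject to Section 5.3.5.6 |

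Two of nine components are secure. For seven of nine, the Adverse Event eCRF is the only evident source at the level of the diagnosis. This is reached by elimination; no section states it.

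**Step 2: does another rule override the exclusion?**

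- Section 5.2.1 counts a new disease as an adverse event, but the same bullet refers the reader to Section 5.3.5.6.
- Section 5.3.5.7 makes a hospitalized event serious only if it is already an adverse event.
- Section 5.3.5.1 prefers a diagnosis to its symptoms, but it governs how an adverse event is named, not whether one is recorded.
- Section 5.3.5.2 in general identifies secondary events by their primary cause. It makes exceptions for severe or serious ones, and for medically significant ones separated in time. Milder complications can be absorbed.
- Section 5.3.5.8 rules out patient-reported data as a back-up.

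None of these clearly overrides the exclusion.

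**Step 3: illustration of size.** Let p be the true proportion of patients with a complication and u the share of those patients left unrecorded. Both are assumptions. Then

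observed proportion = p(1 − u); 95% half-width = 1.96 × √(p(1 − p)/1040).

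The loss, p × u, exceeds the half-width once u > half-width/p.

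| p (patients) | u = 10% | u = 30% | u = 50% | half-width, points | u at which loss = half-width |
|---|---|---|---|---|---|
| 2% (20.8) | 1.8% | 1.4% | 1.0% | 0.85 | 42.5% |
| 3% (31.2) | 2.7% | 2.1% | 1.5% | 1.04 | 34.6% |
| 5% (52.0) | 4.5% | 3.5% | 2.5% | 1.32 | 26.5% |
| 10% (104.0) | 9.0% | 7.0% | 5.0% | 1.82 | 18.2% |

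**Step 4: allow for the secure routes.** Suppose a share h of patients with a complication is counted anyway, through death or hospitalization, and u applies only to the rest. Then

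observed = p[1 − u(1 − h)].

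With p = 3% and h = 50% (an assumption), u = 10% gives 3% × 0.95 = 2.85%, and u = 50% gives 3% × 0.75 = 2.25%. The loss for patients with any complication is half that in Step 3. The gap is therefore mainly in events that led to neither admission nor death.

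**The case against.** The strongest reply is that the protocol never says the endpoint comes from adverse event records. Appendix 1 lists activities rather than eCRF pages: the medical history eCRF (Section 5.3.5.5) and the discontinuation eCRF (Section 4.6.1) have no row there either, so a complications page could exist unseen. This stands. The source is inferred, and if such a page exists the remedy shrinks to naming it.

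Next, the only example in the exclusion is symptom fluctuation, and new myocarditis or sepsis in a convalescent patient plausibly counts as a change in nature. This stands in part. The exception would probably bring in many severe events. But the exclusion covers medical occurrences as well as symptoms, the example does not limit it, and the judgment has no definition behind it.

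Third, the visit form covers urgent care, office and telemedicine visits as well as admissions. Its listed content is a minimum, so a diagnosis may appear as the primary reason. This also stands in part: it narrows the outpatient gap but does not guarantee that the diagnosis is captured.

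Two stronger readings should be resisted. A reader might infer that complications *are* undercounted. The documents do not support that, given the unstated source, the exception and the overlap with the visit form. A reader might also infer that adverse event incidence is biased low. It is not: Section 5.3.5.6 is part of what the protocol counts as a recordable adverse event, so leaving excluded events out follows from the definition. Only uneven application between sites would be a concern there.

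**Conclusion.** The concern holds as a risk to one secondary endpoint. Seven of its nine listed components may be under-ascertained to an unknown, site-dependent degree, mostly where the event leads to neither hospitalization nor death. This rests on the inference that the Adverse Event eCRF is the main source for those seven, and on a reading of the exclusion that its wording permits but does not force.

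The size cannot be established, because the documents give neither a complication rate nor a rate of non-recording. The tabulated figures show only what various assumptions would imply: over true frequencies of 2% to 10%, the loss would exceed the 95% half-width once about 43% down to 18% of affected patients went unrecorded.

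The primary Symptom Diary endpoint is unaffected, and no p-values are planned. The change should still be made, because events that are not recorded cannot be recovered at analysis.

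**What to change.** 1. In Section 5.3.5.6, limit the exclusion to symptom fluctuations that the COVID-19 Symptom Diary captures.
2. In the same section, require every diagnosed COVID-19-related complication to be recorded whether or not it was expected. Name the seven diagnoses and add comparable ones, because the endpoint list gives examples only. Use either the Adverse Event eCRF or a dedicated complications page.
3. Leave death under Section 5.3.5.4, which treats it as an outcome and not an event, and leave COVID-19 hospitalization on the medically-attended-visit form. A blanket rule to record everything in the endpoint list as an adverse event would conflict with Section 5.3.5.4.
4. State the source of each component in the endpoint definition, and carry it into the SAP and the eCRF guide.

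The cost is a short protocol edit, matching eCRF guidance and a few more entries. If the Adverse Event eCRF is used, reported adverse event incidence will rise slightly; a separate page avoids that but adds a form. The change concerns data recording only and does not touch patient management.
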